## **10.3** DEMOGRAPHICS AND BASELINE CHARACTERISTICS

Demographic variables gender, race, ethnicity, and age will be summarized for all enrolled subjects treated with OMNI Surgical System, along with medical history. Descriptive statistical summaries of pre-treatment parameters (min, max, median, mean, standard deviation) will also be provided. The same analyses will be performed for the ITT and PP populations.

#### **10.4** EFFECTIVENESS ENDPOINTS AND ANALYSIS METHODS

Descriptive statistics on continuous variables will include mean, standard deviation, median, minimum, and maximum. Confidence intervals for change from baseline will be included for selected endpoints. Categorical variables will be summarized using frequency counts and percentages. Exact confidence intervals for point estimates may be provided. Statistical testing will be one-sided with a significance level of 0.025 or two-sided significance level of 0.05 unless specify otherwise. Data listings of individual subject data may be provided.

Subjects with washout and those without washout will be analyzed separately.

### **10.5** SAFETY ANALYSIS

All safety analyses will be performed on the ITT population based on all available data descriptively.

#### **10.5.1** Adverse Event

Adverse events (AEs) will be classified as pretreatment, intraoperative or postoperative. The number and the percent of eyes reporting at least 1 adverse event of a given type will be summarized. Additionally, the number of reports of each type of AEs will be provided.

For each AE, the number and the percent of eyes reported with the event will be summarized by the severity level. For eyes with multiple reports of the same type of AE, the maximum severity will be used. Similarly, the AE relationship to the procedure will

be summarized. For eyes with multiple reports of the same type of AE, the closest relationship to the procedure will be used.

# **10.5.2** BEST CORRECTED VISUAL ACUITY (BCVA)

The number and percent of eyes reporting with BCVA of 20/20 or better, 20/25 or better, 20/32 or better, 20/40 or better, worse than 20/40 to 20/80, worse than 20/80 to 20/200, and worse than 20/200 at each visit will be summarized. The number and percent of eyes reporting BCVA of increase  $\geq$  10 letters, increase 10 letters, increase  $\geq$  5 letters to < 10 letters, within 5 letters change, decrease  $\geq$  5 letters to < 10 letters, decrease 10 letters, and decrease  $\geq$  10 letters at each postoperative visit will be calculated.

## 10.5.3 OTHER SAFETY OUTCOMES

The number and percent of eyes reported with each kind of slit lamp findings, gonioscopy findings, and dilated fundus examination findings at each visit will be provided.

The descriptive statistics for the continuous variables will be derived for the visual field mean deviation (MD) and pattern standard deviation (PSD).

## **10.6** INTERIM ANALYSIS

An interim analysis providing descriptive statistics for the outcomes may be completed following completion of the Month 12 follow-up visit by 100% of the enrolled subjects. Endpoints listed below will be analyzed at an interim analysis. No device effectiveness will be claimed based on the interim analysis outcomes.

Subjects with washout and those without washout will be analyzed separately.

Safety endpoints:

CONFIDENTIAL Sight Sciences

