### 4.2 TRAINING

All surgeons would have received training in accordance with Sight Sciences' requirement for using the OMNI Surgical System. OMNI surgery will not be conducted in this trial therefore study specific training on the device will not be required.

The study will employ a medication washout at the 12- and 24-month endpoints only for the subjects that received the OMNI procedure post-medication washout.

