#### 6 STUDY ENDPOINTS

#### 6.1 PRIMARY SAFETY ENDPOINT

Rate of occurrence of sight-threatening adverse events (AEs)

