## 8.7.1 WASHOUT OF HYPOTENSIVE MEDICATIONS

Subjects that had undergone a preoperative medication washout and who are on ocular hypotensive medication at the 12- and 24-month pos-operative visits will be instructed to discontinue their ocular hypotensive medication regimen, and to return for a post-washout visit after completing the appropriate washout period.

Glaucoma medication discontinuation can be staged so that the pressure increase duration is minimized to the greatest possible extent during the washout period. For example, if a patient is on a prostaglandin (PGA) and a Carbonic Anhydrase Inhibitor (CAI), the PGA could be discontinued 4 weeks prior to the Baseline measurement but the CAI allowed to continue until 5 days before Baseline.

If the study subject fails to remember to not use ocular hypotensive medication for the study eye per the required washout period, they can restart washout and return for the appropriate visit upon completion of washout and as long as it falls within the specified visit window. The minimum wash-out periods are specified in Table 2 below.

Brand Name/Chemical Name	Minimum washout period
Carbonic Anhydrase Inhibitors	
Diamox ® (Acetazolamide) – oral Rx	5 days
Neptazane ® (Methazolamide) – oral Rx	5 days
Azopt ® (Brinzolamide)	5 days
Trusopt ® (Dorzolamide Hydrochloride)	5 days
Muscarinic Agonists	
Salagen, Pilocar (Pilocarpine)	5 days
Alpha Adrenergic Agonists	
Alphagan ® (Brimonidine)	14 days
lopidine ® (Apraclonidine Hydrochloride)	14 days
Beta Blockers	
Betagan ® (Levobunolol Hydrochloride)	28 days
Betoptic ® (Betaxalol Hydrochloride)	28 days
OptiPranolol ® (Metipranolol)	28 days
Timoptic/Betimol ® (Timolol Maleate)	28 days
Prostaglandin Analogs	
Lumigan ® (Bimatoprost)	28 days
Travatan ® (Travoprost)	28 days
Xalatan ° (Latanoprost)	28 days
Zioptan ® (Tafluprost)	28 days
Vyzulta® (Latanoprostene Bunod)	28 days
Rho Kinase Inhibitor	
Rhopressa ® (Netarsudil)	28 days
Fixed Combination Medications	
Combigan ® (Brimonidine Tartrate/Timolol Maleate)	28 days
Cosopt ® (Dorzolamide Hydrochloride/ Timolol	28 days
Maleate)	
DuoTrav® (Travoprost/Timolol)	28 days
Ganfort® (Bimatoprost/Timolol)	28 days

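### Does the Month 12 interim need a commitment to a pooled sight-threatening AE rate with an exact confidence interval?

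*Combined protocol and SAP*

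**What the plan says.** All references are to the combined protocol and SAP.

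- **6.1** names one primary safety endpoint: "Rate of occurrence of sight-threatening adverse events (AEs". The public text attaches no expected rate, performance goal or comparator to it.
- **8.3** caps enrolment at 50 subjects with a presurgical washout and 50 without, 100 in all.
- **10.4**, the effectiveness section, states that "Exact confidence intervals for point estimates may be provided". Its only firm interval commitment is for change from baseline on selected endpoints.
- **10.5** states that "All safety analyses will be performed on the ITT population based on all available data descriptively". It does not mention the strata.
- **10.5.1** gives the form of the AE summary: "The number and the percent of eyes reporting at least 1 adverse event of a given type will be summarized".
- **10.6** states that "An interim analysis providing descriptive statistics for the outcomes may be completed following completion of the Month 12 follow-up visit" by all enrolled subjects, that no effectiveness claim will rest on it, and that "Subjects with washout and those without washout will be analyzed separately". A safety subheading comes next; the list under it is not in the public text. The bodies of 10.1 and 10.2 are also absent.

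**The concern.** The study has one primary safety rate and nothing in the public text to compare it with. Its main safety information is therefore the rate and how precisely it is known. Two features seem to weaken this.

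First, the separate-strata sentence in 10.6 stands immediately above the safety subheading, so it is natural to read it as covering safety. No pooled interim rate is mentioned.

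Second, the AE summary is a count and a percent, and the only sentence on exact intervals is permissive and sits under effectiveness. A bare 0% from 50 eyes is compatible with a true rate of about 7%, and a reader shown only the percent might not see that. If two stratum rates were all that was reported, the apparent bound on risk would be nearly twice as wide as the data allow.

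**Working it through.** **Inputs.** Stratum caps of 50 and 50, total 100 (8.3). A two-sided 95% level, consistent with the 0.05 two-sided or 0.025 one-sided rule in 10.4. The plan states no precision figure or expected rate, so there is no figure of its own to reproduce. Event counts and fill levels below are assumptions.

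**Exact (Clopper-Pearson) limits.** For x events in n eyes, the lower limit is the 0.025 quantile of Beta(x, n − x + 1) and the upper limit is the 0.975 quantile of Beta(x + 1, n − x). With x = 0 the lower limit is 0 and the upper limit reduces to 1 − 0.025^(1/n).

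- n = 50: 1 − 0.025^(1/50) = 7.11%
- n = 100: 1 − 0.025^(1/100) = 3.62%
- Ratio: 7.11 / 3.62 = 1.96

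| Assumed result | By stratum | Pooled |
|---|---|---|
| 0 events, 50 + 50 | upper limit 7.11% in each | upper limit 3.62% |
| 0 events, 40 + 40 | upper limit 8.81% in each | upper limit 4.51% |
| 0 events, 50 + 20 | upper limits 7.11% and 16.84% | upper limit 5.13% |
| 1 event in each, 50 + 50 | 0.05% to 10.65% in each | 2/100: 0.24% to 7.04% |

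The arithmetic behind the concern is right. The ratio near 2 is simply the effect of doubling n.

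**Is information lost?** Each subject belongs to one stratum, and 8.5 enrols one eye per subject. The strata do not overlap and their counts add: 1/50 and 1/50 give 2/100, and the pooled interval follows from that fraction alone. Detection is also unaffected. At an assumed true rate of 1%, the chance of at least one event is 1 − 0.99^50 = 39.5% in one full stratum. Across two separate tables it is 1 − (1 − 0.395)² = 63.4%, the same as 1 − 0.99^100 for the pooled table.

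**Does the text exclude a pooled rate?**

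- 10.6 requires separate analysis. It does not say that nothing else will be shown.
- 10.5 covers all safety analyses on the ITT population, with no split and no exception for the interim. The final safety result most naturally reads as pooled.
- Whether the primary safety rate is on the interim list, and in what form, cannot be seen.

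**Do separate safety tables have a purpose?** Yes. Section 4.2 provides for "a medication washout at the 12- and 24-month endpoints only for the subjects that received the OMNI procedure post-medication washout", and 8.7.1 expects pressure to rise meanwhile: "Glaucoma medication discontinuation can be staged so that the pressure increase duration is minimized". A protocol-directed washout in one stratum is a good reason to look at safety by stratum. Section 8.9 lets investigators stop restarted medication in either stratum, so the contrast concerns the scheduled washout only.

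**The case for a change.** The best case for a change is that it costs almost nothing: one table column and one interval from data already collected. The missing interval commitment applies to the final analysis as well as the interim, so it does not depend on whether the interim is run. Settling the presentation in advance also avoids choosing it once events are known, and it tells the programmer whether to build pooled or split tables.

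Part of this stands. No public text commits to an interval for the sight-threatening AE rate, and a pooled rate shown beside the two stratum rates would be useful.

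It does not amount to a fault in the plan. No stated rule produces a wrong number. The comparison of 7.1% with 3.6% sets side by side two intervals that the plan does not promise, so no committed bound is made wider. The interval point comes down to permission rather than obligation in an analysis declared descriptive, and anyone with n/N can compute the interval. Nor is pooling plainly better as the lead result: the strata reflect presurgical practice and fill separately up to their caps, so a pooled rate depends on the mix enrolled and would still need the stratum rates beside it.

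**Conclusion.** No change to the plan follows. Followed as written, it gives correct counts and percents by stratum at an optional, descriptive interim. It also gives a final safety analysis on the ITT population that reads as pooled. The counts add, so a pooled rate and its exact interval can be had at any time.

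The most that could be at stake is an interim upper limit of 7.1% per stratum against 3.6% pooled. That assumes zero events, both strata full at 50, an interim that is actually run, and a report that shows stratum intervals and nothing pooled. With lower assumed enrolment the limits are wider but the point is the same. No error rate, decision rule or effectiveness claim depends on it.

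The conclusion rests on reading 10.5 as unsplit, which is its natural sense though not stated outright. The interim endpoint list and sections 10.1 and 10.2 could not be examined. They might already provide for a pooled rate or an interval, so their absence from the public text is no evidence of a gap.

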## **10.7** DEVIATION FROM THE STATISTICAL PLAN

Any deviations from the statistical plan will be noted in the final report.

### **11 MONITORING PROCEDURES**

Sight Sciences or contract research organization (CRO) personnel will monitor the study in a manner consistent with FDA regulations, good clinical practices and the clinical research standards adopted by Sight Sciences. Study monitoring will be executed using on-site and remote monitoring visits as needed and as determined by the study team. The frequency and necessity of visits will be determined by the study team. Study monitoring will involve the following elements:

- Site Qualification: Sight Sciences or CRO personnel will meet with investigators and clinical study staff prior to the initiation of the study in order to review the adequacy of the subject population, facilities, and equipment with respect to the needs of the study, and to familiarize the investigator with the study protocol. If Sight Sciences or the CRO have recently been involved with an investigator for another study, a site qualification visit may not be necessary.
- Site Initiation: Sight Sciences and/or CRO personnel will meet with the investigator(s) and clinical study staff when the site is ready to begin enrolling subjects in order to train them in how to properly select subjects, perform the study procedure, and record study data. The site initiation visit may be conducted remotely and may include a grouping of multiple sites. This visit will include, but not be limited to a review of the following:
  - o Detailed review of the protocol
  - Informed consent procedures
  - Instructions for the surgical procedure
  - o Records and reports
- Interim Monitoring: Sight Sciences or CRO personnel will conduct routine visits during the course of the study to review charts, perform source document verification, ensure proper adherence to the study protocol, and to review regulatory documents. Interim monitoring visits and telephone consultation

will occur as necessary during the course of the study to ensure the proper progress and documentation of the study findings.

- Study Close Out Visit: At the conclusion of the trial there will be a study closure visit during which several actions, including but not limited to the following, will be performed:
  - A final inspection of the study binder
  - Accountability and return of all devices and non-consumable ancillary study supplies to the sponsor
  - $\circ$   $\;$  Discussion of record retention requirements with the investigator
  - Close-out notification to the IRB

# 12 DATA AND QUALITY MANAGEMENT

## **12.1 DATABASE MANAGEMENT**

The study database will be designed using an electronic data capture (EDC) system that is compliant with 21 CFR Part 11 and relevant guidance documents. The EDC will be developed and maintained by an independent, qualified data management firm.

The database will incorporate time-stamped audit trails, protection of human subjects, restricted access, and data security at the component level. Each database module, including each individual eCRF, will be validated by conducting a series of standard tests that demonstrate usability and correctness of the database system. The database will be maintained on an ongoing basis and will be routinely backed up.

## **12.2** SUBJECT IDENTIFICATION

The subjects will be identified by a six-digit subject number composed of a double-digit study identification number, a two-digit center identification number followed by a three-digit sequential subject number. A subject identification number will be assigned after informed consent is obtained. This will ensure that identifiable subject information has been removed and kept confidential.

## **12.3** SUBJECT ACCOUNTABILITY

All subjects enrolled in this clinical investigation shall be monitored for the duration of the investigation. The clinical investigation shall be considered completed when all subjects that have been enrolled in the investigation have reached the final reporting period, excluding subjects who were withdrawn.

## **12.4 CONFIDENTIALITY**

All medical records associated with the clinical investigation will be made available for review by Sight Sciences personnel, its contract research organization (CRO) and

governmental/regulatory agencies involved. The results of the study may be published in the future for scientific and marketing purposes, but the identity of each subject will not be revealed. All records will be stored in a secure area at the investigator's facility, the CRO, the data management firm and at Sight Sciences, Inc.

# **12.5** Source Data and Case Report Forms

Source data will be entered into a validated electronic system at each site by trained personnel in accordance with 21 CFR Part 11 requirements. Electronic entries will be verified against corresponding source data at the sites and queried/corrected if needed to the extent possible. Medical site records serve as source data. In addition, data that are collected exclusively for the purpose of this study and not normally recorded in the subjects' medical records can be collected directly on any study CRFs or tools provided by the sponsor, and these will serve as the source data.

Source data and study CRFs are to be maintained at the site in the subject records or in the medical records. All data entries must be made in accordance with ALCOA (Attributable, Legible, Contemporaneous, Original, Accurate) standards and GDP (Good Documentation Practices).

Study data acquired from sites will be collected on Electronic Case Report Forms (eCRFs) for submission to sponsor. Sites will enter data entered on source documents into the electronic case report forms for Sponsor review and analysis.

## **12.6 RETENTION PERIOD**

Clinical sites are to retain any and all clinical trial material (documentation, photographs, etc.) for a period of two years from the date a marketing application is approved or two years after the investigation has been discontinued, or as directed by their institutional document retention requirements, whichever is the longest. After that time, the items must be returned to Sight Sciences for archiving.

## **13** PROTOCOL MODIFICATIONS AND DEVIATIONS

Protocol modifications may occur during the study. Each will be approved by the sponsor before implementation. Each will undergo Institutional Review Board (IRB) review and approval, as necessary.

Any deviations from this protocol intended to protect the life or physical well-being of a subject in an emergency are to be reported to Sight Sciences, Inc. as well as the IRB as soon as possible, and no later than 5 working days after the emergency occurred.

All protocol deviations will be documented using the Protocol Deviation CRF or Source Tool.

## **14 ETHICAL CONSIDERATIONS**

### **14.1** DECLARATION OF HELSINKI

This study shall be conducted in accordance with the Declaration of Helsinki (Appendix D).

## 14.2 INSTITUTIONAL REVIEW BOARDS (IRB)

The study shall not begin at a site until approval has been obtained from the reviewing IRB. It is the Investigators' responsibility to obtain and maintain written approval of the study protocol and Informed Consent documents from the appropriate IRB. It is also the Investigators' responsibility to notify and obtain approval from (if needed) that body about any amendments to these documents and to follow the IRBs rules regarding the reporting of Adverse Events and Protocol Deviations related to the investigational device and/or this study. Copies of all written approvals (identifying the study, the submitted and approved documents and the date reviewed) and the approved versions of the documents must be provided to Sight Sciences or its CRO.

The Investigators must file all correspondence with the IRB and forward copies of such correspondence to Sight Sciences.

## 14.3 INFORMED CONSENT DOCUMENT (ICD)

An Informed Consent template that covers all protocol procedures and follows GCP Guidelines will be prepared by Sight Sciences and made available to each Investigator. The Investigator may adapt these templates to the requirements of the local IRB and of the institution where the study is conducted, but any revisions made to the ICD must be submitted to the sponsor for review prior to submission to the IRB. A copy of each IRBapproved ICD version is to be made available to Sight Sciences and its CRO. The approved, IRB-stamped ICD is to be kept in its full length in the study Regulatory Binder. Original, signed ICDs are to be maintained in study records and must be made available for monitoring review.

## 14.4 PUBLIC LISTING OF STUDY

The study will be listed on the NIH website www.clinicaltrials.gov.

## **15 STUDY ADMINISTRATION**

#### **15.1** EARLY TERMINATION OR SUSPENSION OF THE STUDY OR AN INVESTIGATIONAL SITE

Sight Sciences may terminate the study, in which case the investigators and associated IRBs will be notified in writing. Possible reasons for study termination include but are not limited to:

- The discovery of an unexpected, significant, or unacceptable risk to the study subjects implanted with the device
- Withdrawal of FDA clearance of the OMNI device.
- Insufficient enrollment in the study
- The Sponsor determines that enough data has been collected for the study, and no further data are needed.

Sight Sciences reserves the right to stop the study at a particular site any time after the initiation visit if there have been no subject enrollments or if there have been significant protocol deviations/violations at the site.

Likewise, a principal investigator may terminate the study at his/her institution. This decision must be followed by written notification to Sight Sciences within five working days, stating the reasons for termination.

If the study is terminated, every effort should be made to obtain final follow-up from all subjects.

In the event that there are significant human use issues with the device, the investigator will be consulted to make a determination of whether the study should be terminated or not.

### **15.2** INVESTIGATOR RESPONSIBILITIES

#### **15.2.1** GENERAL RESPONSIBILITIES OF INVESTIGATORS

An Investigator is responsible for ensuring that an investigation is conducted according to the signed agreement, the investigational plan and applicable FDA regulations, for protecting the rights, safety, and welfare of subjects under the Investigator's care, and for the control of devices under investigation. An Investigator also is responsible for ensuring that informed consent is obtained in accordance with 21 CFR part 50.

